6.7.3. External Support

As listed above, the status of the subject using external support will be evaluated at the preoperative visit and at 3 months, 6 months and 12 months. The within subject changes from visit to visit will be analyzed in addition. This analysis is part of the final report.

The variable capturing "Is the subject using an external support" will be used and recoded into a new variable for each visit with the options "no" (using no support at all) versus "yes" (including Walker, Cane, One Crutch or Two Crutches).

Evaluation Variable / Question	Level of Measurement	Recoding
All Assessments – Extern	al support stati	18
Recode initial external support status at pre-op visit into new variable "Pre- Op External Support Dichotomous" (Variable(s): EXTRSUPP)	Qualitative, nominal	The variable capturing "Is the subject using an external support" will be used and recoded into a new variable for each visit with the options "no" (using no support at all) versus "yes" (including Walker, Cane, One Crutch or Two Crutches).
Recode initial external support status at pre-op visit into new variable "3	Qualitative, nominal	The variable capturing "Is the subject using an external support" will be used and recoded into a new variable for each visit with the options "no" (using no support at all)

Months External Support Dichotomous" (Variable(s): VISITDT; EXTRSUPP)		versus "yes" (including Walker, Cane, One Crutch or Two Crutches).
Recode initial external support status at pre-op visit into new variable "6 Months External Support Dichotomous" (Variable(s): VISITDT; EXTRSUPP)	Qualitative, nominal	The variable capturing "Is the subject using an external support" will be used and recoded into a new variable for each visit with the options "no" (using no support at all) versus "yes" (including Walker, Cane, One Crutch or Two Crutches).
Recode initial external support status at pre-op visit into new variable "12 Months External Support Dichotomous" (Variable(s): VISITDT; EXTRSUPP)	Qualitative, nominal	The variable capturing "Is the subject using an external support" will be used and recoded into a new variable for each visit with the options "no" (using no support at all) versus "yes" (including Walker, Cane, One Crutch or Two Crutches).

Table 6.7.3.1: All Assessments – External Support Recoding

New variables (10) will then be created for each comparison listed below. Negative changes (from "no" to "yes") will be coded with "negative change" and positive changes (from "yes" to "no") with be coded with "positive change". If there is no change (from "yes" to "yes" or from "no" to "no"), the coding will be "no change".

Evaluation	Level of Massurement	Coding and Analysis Plan
All Assessments - Exter	measurement	16
Create new variable "External support status change between pre- operative visit and 3 months" based on comparison of "Pre-Op External Support Dichotomous" with "3 Months External Support Dichotomous" (Variable(s): VISITDT; EXTRSUPP)	Qualitative, nominal	 Negative changes (from "yes" to "no") = "negative change" Positive changes (from "no" to "yes") = "positive change" No change (from "yes" to "yes" or from "no" to "no") = "no change" Proportions, frequencies, column and row totals, missing proportion (if any).
Create new variable "External support status change between pre- operative visit and 6 months" based on comparison of "Pre-Op External Support Dichotomous" with "6 Months External Support Dichotomous" (Variable(s): VISITDT; EXTRSUPP)	Qualitative, nominal	 Negative changes (from "yes" to "no") = "negative change" Positive changes (from "no" to "yes") = "positive change" No change (from "yes" to "yes" or from "no" to "no") = "no change" Proportions, frequencies, column and row totals, missing proportion (if any).
Create new variable "External support status change between pre- operative visit and 12 months" based on comparison of "Pre-Op External Support Dichotomous" with "12 Months External Support Dichotomous" (Variable(s): VISITDT; EXTRSUPP)	Qualitative, nominal	 Negative changes (from "yes" to "no") = "negative change" Positive changes (from "no" to "yes") = "positive change" No change (from "yes" to "yes" or from "no" to "no") = "no change" Proportions, frequencies, column and row totals, missing proportion (if any).
Create new variable "External support status change between 3 months and 6 months" based on comparison of "3 Months External Support Dichotomous" with "6	Qualitative, nominal	 Negative changes (from "yes" to "no") = "negative change" Positive changes (from "no" to "yes") = "positive change" No change (from "yes" to "yes" or from "no" to "no") = "no change"

Months External Support Dichotomous" (Variable(s): VISITDT; EXTRSUPP)		Proportions, frequencies, column and row totals, missing proportion (if any).
Create new variable "External support status change between 3 months and 12 months" based on comparison of "3 Months External Support Dichotomous" with "12 Months External Support Dichotomous" (Variable(s): VISITDT; EXTRSUPP)	Qualitative, nominal	 Negative changes (from "yes" to "no") = "negative change" Positive changes (from "no" to "yes") = "positive change" No change (from "yes" to "yes" or from "no" to "no") = "no change" Proportions, frequencies, column and row totals, missing proportion (if any).
Create new variable "External support status change between 6 months and 12 months" based on comparison of "6 Months External Support Dichotomous" with "12 Months External Support Dichotomous" (Variable(s): VISITDT; EXTRSUPP)	Qualitative, nominal	 Negative changes (from "yes" to "no") = "negative change" Positive changes (from "no" to "yes") = "positive change" No change (from "yes" to "yes" or from "no" to "no") = "no change" Proportions, frequencies, column and row totals, missing proportion (if any).

Table 6.7.3.2: All Assessments – External support status Tables List

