11.3.4. Additional Analyses

Additional Analyses are outlined in the subsequent sections. Analysis details (variables, level of measurement, planned steps) are listed in-depth in the SAP.

Weight-bearing status

The weight bearing status will be evaluated and analyzed at the pre-operative visit and at 3 months, 6 months and 12 months. The within subject changes from visit to visit will be analyzed in addition. This analysis will be part of the annual and final reports.

External Support

The status of the subject using external support will be evaluated at the pre-operative visit and at 3 months, 6 months and 12 months. The within subject changes from visit to visit will be analyzed in addition. This analysis will be part of the annual and final reports.

Mortality

For analysis of the time to death or mortality, the Kaplan-Meier method will be used. The times between the date of surgery and the date of the 12 months assessment will be used together with the times between surgery and the date of death. This analysis will be part of the annual and final reports.

Reoperation

For analysis of the time to the reoperation, the Kaplan-Meier method will be used. The times between the date of surgery and the date of the 12 months assessment will be used together with the times between date of surgery and the date of reoperation (earliest reoperation in case that one subject experienced more than one reoperation). This analysis will be part of the annual and final reports.

SF-36 Total Score – Within subject changes by visit

The within subject score changes of the SF-36 Total Score from visit to visit will be analyzed to help identify the changes on the subject level. This analysis will be part of the annual and final reports.

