Creation of variable Number of previous history of surgery to the Contralateral Tibia by Subject (Variable(s): CONTRPROCNM1; CONTRPROCNM2; CONTRPROCNM3; CONTRPROCNM4)	Qualitative, nominal	Proportions, frequencies, column and row totals, missing proportion (if any).		x	
Weight Bearing (Variable(s): WEIGTBEAR)	Qualitative, nominal	Proportions, frequencies, column and row totals, missing proportion (if any).	X	X	
Weight Bearing Specification (Variable(s): WEIGTSPC)	Qualitative, nominal	Proportions, frequencies, column and row totals, missing proportion (if any).	X	X	
External Support Prior to the Tibia Fracture (Variable(s): EXTRSUPP)	Qualitative, nominal	Proportions, frequencies, column and row totals, missing proportion (if any).	X	Х	

Table 6.2.4: Pre-Operative Visit Form – Subject Evaluation Tables List

Evaluation Variable / Question	Level of Measurement	Analysis Plan	Inclusion		
Pre-Operative Visit Form – SF-36 Score (post fracture, prior to					N/A
surgery)			ш	ΓN	
In general, would you say your	Oualitative.	Proportions, frequencies,			
health is (Variable(c): GH01 PESPONSE)	nominal	column and row totals,			X
Compared to one year ago, how		missing proportion (if any).			
would you rate your health in	Qualitative,	Proportions, frequencies,			37
general now?	nominal	column and row totals,			X
(Variable(s): HT_RESPONSE)		missing proportion (if any).			
Vigorous activities, such as running,		Proportions, frequencies,			
lifting neavy objects, participating in strenuous sports	Qualitative,	column and row totals,			Х
(Variable(s): PF01 RESPONSE)	nommar	missing proportion (if any).			
Moderate activities, such as moving a		Proportions fraguencies			
table, pushing a vacuum cleaner,	Qualitative,	column and row totals			x
bowling, or playing golf	nominal	missing proportion (if any).			
(Variable(s): PF02_RESPONSE)		Proportions fraguencies			
Lifting or carrying groceries	Qualitative,	column and row totals.			x
(Variable(s): PF03_RESPONSE)	nominal	missing proportion (if any).			
Climbing soveral flights of stairs	Qualitative	Proportions, frequencies,			
(Variable(s): PF04 RESPONSE)	nominal	column and row totals,			Х
	nominar	missing proportion (if any).			
Climbing one flight of stairs	Qualitative,	Proportions, frequencies,			v
(Variable(s): PF05_RESPONSE)	nominal	missing proportion (if any)			л
		Proportions, frequencies.			
Bending, kneeling, or stooping	Qualitative,	column and row totals,			Х

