6.5. POST-OPERATIVE CHARACTERISTICS

The analysis of the Postoperative data must be performed separately for each follow-up visit listed in table 4.4 in accordance to the following tables in this chapter. New Variables must be created individually for each follow-up visit.

Evaluation	Level of						
Variable / Ouestion	Measurement	Analysis Plan	I	nclusio	n		
Post-Operative Visit Form – Ph	ysical Exam		IR	FR	N/A		
Date of Visit:	Date/Time	None			Х		
Creation of variable Difference between Date of Surgery [dd.mm.yyyy] and Date of Visit [dd.mm.yyyy] In [days] (Variable(s): VISITID; VISNAME)	Case summary with number and percentage of valid cases/values, missing cases/values (if any) and total cases/values.Quantitative, ratioMean, median, interquartile range, maximum, minimum, standard deviation, 95% confidence interval for mean, Shapire Wilk Tast		Quantitative, ratio Quanti			х	
Is the subject weight bearing? (Variable(s): WEIGHTBEAR)	Qualitative, nominal	Proportions, frequencies, column and row totals, missing proportion (if any).	Х	Х			
Specify, Full or Partial (Variable(s): FULPART)	Qualitative, nominal	Proportions, frequencies, column and row totals, missing proportion (if any).	Х	Х			
Is the subject using an external support? (Variable(s): EXTRSUPP)	Qualitative, nominal	Proportions, frequencies, column and row totals, missing proportion (if any).	X	Х			
Has the bone consolidated (consider weight-bearing, pain and imaging)? (Variable(s): BONECONS; EXPLN)	Qualitative, nominal	Proportions, frequencies, column and row totals, missing proportion (if any). Listing of given explanations.	Х	Х			

Table 6.5.1: Post-Operative Visit Form – Physical Exam Tables List

Evaluation	Level of Massurament			clusion	
Post-Onerative Visit Form – SF	-36 Score		IR	FR	N/A
In general, would you say your health is (Variable(s): GH01 RESPONSE)	Qualitative, nominal	Proportions, frequencies, column and row totals, missing proportion (if any).			X
Compared to one year ago, how would you rate your health in general now? (Variable(s): HT RESPONSE)	Qualitative, nominalProportions, frequencies, column and row totals, missing proportion (if any).				х
Vigorous activities, such as running, lifting heavy objects, participating in strenuous sports (Variable(s): PF01_RESPONSE)	Qualitative, nominalProportions, frequencies, column and row totals, missing proportion (if any).				Х

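### External support is recorded as status before the fracture but analysed and titled as status at the pre-operative visit in three of six change tables

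*SAP*

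**What the plan says.** The baseline item is in SAP 6.2, Table 6.2.4, on the pre-operative form: "External Support Prior to the Tibia Fracture", stored as EXTRSUPP. It is the only external-support item listed for that form.

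The follow-up item, in SAP 6.5, Table 6.5.1, has the same variable name but asks about current use: "Is the subject using an external support? (Variable(s): EXTRSUPP".

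The analysis text treats both as status at a visit. SAP 6.7.3 states that "the status of the subject using external support will be evaluated at the preoperative visit and at 3 months, 6 months and 12 months". CIP 11.3.4 says "The status of the subject using external support will be evaluated at the pre-operative visit", and SAP 3.1.3 repeats this. The baseline row of Table 6.7.3.1 reads "Recode initial external support status at pre-op visit into new variable" and gives the current-use question as its source. Table 6.7.3.2 then lists six change variables. Three start from baseline, the first being "External support status change between pre- operative visit and 3 months"; the other two run to 6 and 12 months.

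Under the coding rule, yes-to-yes and no-to-no both count as *no change*.

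**The concern.** The item and the table title refer to different times, and the fracture falls between them. Someone who walked unaided until the injury may well need support when seen before surgery, so the two statuses cannot be assumed equal.

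A reader of the final report would take the three tables at their word, as movement since the pre-operative visit. The data show something else: whether the subject is back at the level of support used before the fracture. Both questions are reasonable, but they have different answers.

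The SAP draws this distinction elsewhere. The heading of Table 6.2.5 places the baseline SF-36 after the fracture and before surgery, and SAP 6.7.6 titles its SF-36 changes as starting from the pre-operative visit. The report would thus carry two sets of change tables with the same starting label, one from a post-fracture baseline and the other from a pre-fracture baseline.

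**Working it through.** No sample-size or power formula applies. The check counts the comparisons and follows the coding rule through every response pattern.

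**1. Number of tables.** There are four time points: baseline, 3, 6 and 12 months. Pairs: 4 × 3 / 2 = 6. SAP 6.7.3 announces 10 new variables, which does not reproduce; ten pairs would need five time points (5 × 4 / 2 = 10). Table 6.7.3.2 lists six, and three of them use the baseline.

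**2. Recorded versus titled comparison.** The table below takes the 12-month comparison; 3 and 6 months work the same way. Status at the pre-operative visit is hypothetical, since no listed item captures it.

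| Before fracture (recorded) | At pre-op visit (not recorded) | 12 months | Result from the recorded item | Result the title implies |
|---|---|---|---|---|
| no | yes | no | no change | stopped support |
| no | yes | yes | started support | no change |
| no | no | no | no change | no change |
| no | no | yes | started support | started support |
| yes | yes | no | stopped support | stopped support |
| yes | yes | yes | no change | no change |
| yes | no | no | stopped support | no change |
| yes | no | yes | no change | started support |

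The result differs from the title in 4 of 8 patterns, exactly those in which status before the fracture and status at the visit differ. The first row is the case of main interest: unaided before, on support when seen before surgery, unaided again at 12 months. The second row errs the other way, since continued use since the visit is shown as a change. These are counts of patterns, not of subjects.

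**3. Sign of a change.** The two parts of SAP 6.7.3 disagree:

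| Movement | Narrative before Table 6.7.3.2 | Every row of Table 6.7.3.2 |
|---|---|---|
| no to yes (starts support) | negative | positive |
| yes to no (stops support) | positive | negative |

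The table rows match those of the weight-bearing table (6.7.2.2), where yes-to-no is the unfavourable direction. For external support the narrative calls it favourable. The *no change* result in step 2 is the same under either version; the direction of any change is not.

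**The case against.** The strongest defence is that the pre-operative visit is partly a form name. SAP 4.4 says that pre-operative data may be recorded after surgery and that the SAP follows the labels of the EDC export. CIP 10.3 allows the initial assessment up to 3 months after surgery, with retrospective collection. On that view, evaluated at the visit means only asked on that form, and Table 6.2.4, which goes into both interim and final reports, shows the true wording of the item. In addition, the phrase about status at the pre-op visit recurs in the follow-up rows of Table 6.7.3.1, so it looks copied and is weak evidence of timing on its own. This explains how the label may have arisen. It does not cure titles that state a change between the pre-operative visit and a later month, and no section says that the baseline is pre-fracture.

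It is also fair to say that a pre-fracture reference is legitimate, and that *no change* is then the correct code for return to prior function. That stands: the fault is in the description and titles, not in the choice of reference.

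A reader might go further and infer that crutches at 3 months are coded as a worsening, or that only subjects who used support before the injury can ever be coded as improved. The documents do not support either as a general statement. Both follow the narrative rule alone; under the rows of Table 6.7.3.2, starting support is coded positive. Nor can a share of subjects be attached, because no rate of prior support use is given.

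**Conclusion.** The mismatch is real and should be corrected. Three of the six external-support change tables carry a title that their data do not match, and a subject unaided before the fracture and unaided again at follow-up is shown as unchanged since the pre-operative visit. This rests on Table 6.2.4 listing the only external-support item on the pre-operative form; CIP section 11 says that the SAP lists all variables, which supports that reading. If the CRF holds a separate item for status at the visit, the fault is instead that the SAP does not cite it.

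The conclusion does not extend to a biased direction of change or to a numerical limit on improvement, because the sign rule is itself contradictory. The number of misdescribed subjects is unknown. The consequence is confined to descriptive frequencies in an additional analysis: no hypothesis test is attached to it, and the primary endpoint, its test and the sample size are unaffected.

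**What to change.** 1. In CIP 11.3.4, SAP 3.1.3 and SAP 6.7.3, name the baseline *pre-fracture external support (EXTRSUPP, Table 6.2.4)*. If the CRF has a separate item for status at the pre-operative visit, cite that item instead and keep the titles.
2. Retitle the three baseline tables as comparison with pre-fracture status at 3, 6 and 12 months, with levels *same as*, *less support than* and *more support than before fracture*. State that *same* includes return to prior function. Three levels are better than a yes/no return variable, which would not separate less support than before from no change.
3. Make Table 6.7.3.2 agree with the narrative for all six comparisons. Stopping support is positive (less support, in the three baseline tables) and starting support is negative (more support). Without this step the 3-to-6, 3-to-12 and 6-to-12 month tables stay contradictory even after the baseline is renamed.
4. Change the announced number of new variables from 10 to 6, and correct the follow-up rows of Table 6.7.3.1 that refer to status at the pre-op visit.

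The cost is wording, three retitled derived variables and corrected coding in six table rows, with no new data. CIP section 15 sends amendments to the ethics board, so the CIP wording carries that administrative step; the SAP edits do not change the CIP text.

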6.7.2. Weight-bearing status

As listed above, the weight bearing status will be evaluated and analyzed at the preoperative visit and at 3 months, 6 months and 12 months. The within subject changes from visit to visit will be analyzed in addition. This analysis is part of the final report.

The variable capturing weight bearing will be used with "yes" (including partial and full) versus "no" weightbearing.

Evaluation	Level of	Recoding
Variable / Question	Measurement	Recouning
All Assessments - Weight-b	earing status	
Recode initial weightbearing status at pre-op visit into new variable " Pre- Op Weightbearing Dichotomous " (Variable(s): VISITDT; WEIGHTBEAR)	Qualitative, nominal	The initial variable capturing weight bearing pre- op will be recoded with "yes" (including partial and full) versus "no" weightbearing.
Recode initial weightbearing status at pre-op visit into new variable "3 Months Weightbearing Dichotomous" (Variable(s): VISITDT; WEIGHTBEAR)	Qualitative, nominal	The initial variable capturing weight bearing at 3 months will be recoded with "yes" (including partial and full) versus "no" weightbearing.
Recode initial weightbearing status at pre-op visit into new variable "6 Months Weightbearing Dichotomous" (Variable(s): VISITDT; WEIGHTBEAR)	Qualitative, nominal	The initial variable capturing weight bearing at 6 months will be recoded with "yes" (including partial and full) versus "no" weightbearing.
Recode initial weightbearing status at pre-op visit into new variable "12 Months Weightbearing Dichotomous" (Variable(s): VISITDT; WEIGHTBEAR)	Qualitative, nominal	The initial variable capturing weight bearing at 12 months will be recoded with "yes" (including partial and full) versus "no" weightbearing.

Table 6.7.2.1: All Assessments – Weight-bearing status Recoding

New variables (10) will then be created for each possible pair/comparison. Negative changes (from "yes" to "no") will be coded with "negative change" and positive changes (from "no" to "yes") with be coded with "positive change". If there is no change (from "yes" to "yes" or from "no" to "no"), the coding will be "no change".

Evaluation Variable / Question	Level of Measurement	Coding and Analysis Plan
All Assessments - Weight-bearing statu	15	

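### SAP Table 6.7.3.2 codes external-support changes in the opposite direction to the text above it, so stopping crutches would be reported as a negative change

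*SAP*

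**What the plan says.** SAP section 6.7.3 (External Support) gives three instructions that have to work together.

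- **Meaning of the states.** The recoded variable at each visit is "no' (using no support at all) versus 'yes' (including Walker, Cane, One Crutch or Two Crutches". *Yes* therefore means that the subject depends on a walking aid.
- **Coding rule in the text.** The paragraph before Table 6.7.3.2 states "Negative changes (from 'no' to 'yes') will be coded with 'negative change", and then "positive changes (from 'yes' to 'no') with be coded with 'positive change".
- **Coding rule in the table.** Every row of Table 6.7.3.2 states "Negative changes (from 'yes' to 'no') = 'negative change" and "Positive changes (from 'no' to 'yes') = 'positive change".

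The table has six rows: pre-operative to 3, 6 and 12 months, 3 to 6 months, 3 to 12 months, and 6 to 12 months. All six carry the same rule. The paragraph also announces the number of variables: "New variables (10) will then be created for each comparison listed below".

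The neighbouring section 6.7.2 (Weight-bearing status) uses this same rule in both its text and Table 6.7.2.2: "Negative changes (from 'yes' to 'no') will be coded with 'negative change". There *yes* means that the subject bears weight, so the rule fits.

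**The concern.** One section gives two opposite rules for the same derived variables. The text agrees with the SAP's definition of *yes*; the table does not.

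The table is not a mere illustration. The opening of SAP section 6 says that the tabulated plan sets out the variables and how each is analysed. The relevant column of Table 6.7.3.2 is headed as the coding and analysis plan, and each row tells the programmer to create a variable. Someone programming the report could reasonably work from the table alone.

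In that case recovery is reported as deterioration: a subject on crutches at 3 months who walks unaided at 12 months is a negative change. The reverse error affects the comparisons with baseline. The pre-operative item in Table 6.2.4 asks about support before the fracture, so a subject who needed none then and uses crutches at 3 months would be shown as a positive change. Table 6.7.2.2 uses the same labels correctly, so two adjacent measures of recovery would point in opposite directions for the same patient.

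**Working it through.** The plan gives no figure to reproduce. The check lists every possible transition under each rule and then counts the comparisons affected.

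**Step 1. Transitions.** Two states at each of two visits give four transitions.

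| Earlier to later visit | Meaning | Text of 6.7.3 | Table 6.7.3.2 | Agree? |
|---|---|---|---|---|
| no to yes | starts using support | negative | positive | No |
| yes to no | stops using support | positive | negative | No |
| yes to yes | still using support | no change | no change | Yes |
| no to no | still unsupported | no change | no change | Yes |

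Both transitions that involve a change conflict. Both that involve none agree.

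**Step 2. Comparisons affected.** Visits are pre-operative, 3, 6 and 12 months. The number of pairs is 4 × 3 / 2 = 6, which matches the six rows printed. All six carry the reversed rule, so 6 of 6 comparisons are affected. The announced 10 does not match; it would be the number of pairs among five visits, 5 × 4 / 2 = 10. Section 6.7.2 also announces 10 and lists six.

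**Step 3. Effect on the reported percentages.** Let *a* subjects stop support, *b* start and *c* stay the same, with N = a + b + c.

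- Text rule: positive = a/N, negative = b/N.
- Table rule: positive = b/N, negative = a/N.
- Positive minus negative is (a − b)/N under the text and −(a − b)/N under the table. The unchanged share, c/N, is the same under both.

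**Step 4. Illustrations.** The documents give no expected counts for external support, so the counts below are assumptions.

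- N = 61 (the SAP's sample size before allowance for drop-out), a = 40, b = 3, c = 18. Text: 40/61 = 65.6% positive and 3/61 = 4.9% negative. Table: 4.9% positive and 65.6% negative. Unchanged under both: 18/61 = 29.5%.
- N = 80 × (1 − 0.20) = 64 (planned enrolment less the assumed drop-out), a = 50. Stopping support is 50/64 = 78% positive under the text and 78% negative under the table.

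The full swap of the two categories does not depend on these counts; only the percentages do.

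**The case against.** Four points can be made on the other side.

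1. **Nothing has been misreported yet.** The correct rule stands directly above the table, and no provision says that a table overrides adjacent text. This stands: the consequence is conditional on the table being followed. It does not remove the fault, because the SAP is equally silent on the text overriding the table.

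2. **The reach is small.** External support is an additional, descriptive analysis of frequencies and proportions, without a hypothesis test. The primary SF-36 PCS comparison, bone consolidation and device-related adverse events do not use it. This also stands and limits the weight of the point.

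3. **A careful reader could notice.** Support status itself is tabulated before the fracture (Table 6.2.4) and at each follow-up visit (Table 6.5.1). If use of support falls while the change table shows mostly negative changes, the mismatch is visible, and the underlying data are intact. That is a useful check, but it relies on someone comparing tables. The row totals and missing counts would still add up, so a routine totals check would not find the error.

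4. **The worked percentages are invented.** They are assumed, and the real denominators are uncertain. External support sits on the physical examination form, while subjects whose fracture has already consolidated give the SF-36 by phone. The documents do not say whether external support is asked in that call. The percentages are therefore illustrations only.

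None of these points reconciles the two rules. The same complete rule printed six times is not a text-extraction fault.

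**Conclusion.** The concern holds. Table 6.7.3.2 contradicts both the coding paragraph above it and the SAP's definition of external support. If the table is followed, both change categories are swapped in six of six comparisons, for every subject whose status changes; the unchanged category is right.

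This rests on the SAP's own definitions and on no outside figure. It assumes only that a programmer might work from the table. That the wording was carried over from the weight-bearing table is likely, since the rule is the same, but this is an inference and the conclusion does not need it.

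The effect is confined to a descriptive analysis. The SAP places it in the final report; protocol section 11.3.4 places it in the annual reports as well. It should be corrected, but it does not threaten the trial's main conclusion.

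**What to change.** In all six rows of SAP Table 6.7.3.2, define *no* to *yes* as negative change and *yes* to *no* as positive change, as the text of section 6.7.3 already does. Leave the no-change definition as it is, and leave Table 6.7.2.2 alone, because its rule is right for weight-bearing.

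In the same edit, change the announced number of new variables from 10 to 6 in section 6.7.3, and also in section 6.7.2, where the same miscount appears.

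The cost is one table edit and two corrected numbers in a SAP revision, with no new data and no change to any other analysis. If programming has already been done, check which rule the code applies, and compare the change table with the visit-by-visit support frequencies before the report is released.
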